For rare instances or emergency cases, the *Pharmacy Guidelines and Instructions for DAIDS Clinical Trials Networks* permits shipment by mail or courier of study product from the site directly to participants. This method should only be used on a short-term basis and if permissible by the site's institution. If this method is to be implemented, each site's Pharmacist of Record (PoR) must develop appropriate procedures for the shipment or courier of study product to identified participants in accordance with these guidelines, and document chain of custody. Prior to implementation, the site PoR must coordinate with site clinic staff to determine the appropriateness of this method for applicable protocols and participants.

4. In section 6.1, Schedule of Evaluations, the visit window for weeks 36 to 96 has been changed as shown below:

Evaluation	Screening	Pre-Entry	Entry	Post-Entry Evaluations (Weeks)									Confirmation of VF	Premature Study/Treatment Discontinuation
				2	4	12	24	36	48	60	72	84		
Visit Windows				± 1 wk	± 2 wks			- 4 wks, + 8	12 wks					

5. In section 6.2.3, Post-Entry Evaluations, the following instructions have been added to the On-Treatment Evaluations subsection:

Alternate Completion of Post-Entry Evaluations

- **If the participant's visit is postponed within the extended visit window, the site should ensure that the participant has sufficient supply of the study products to last him or her to the point when he or she can come to the clinic.**
- **If the participant does not have enough supply of study products to allow the visit to be postponed, the site must attempt to contact the participant by phone or other method available.**
 - During the remote contact for visit week 72 or week 96, the site should conduct a safety follow-up (such as inquiring about signs and symptoms) to determine if any AEs or serious adverse events (SAEs) have occurred since the last visit and if the participant needs medical follow-up. Additionally, the site should complete the questionnaires and adherence assessment per section 6.3.9, section 6.3.10, and MOPS section 4. All other evaluations and stored samples that will be missing for the visits, and the reason why they are missing, must be documented in the participant's study file.
 - At all visits except week 96, the site should confirm if the participant is able to

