2.4 Overview of Sample Size Considerations

Based on previous studies, a standard deviation (SD) of 0.7 in the 48-week change in normalized neurocognitive test score is assumed. In the sample size calculation, the null hypothesis is that there is no difference in changes of neurocognitive functioning from baseline to week 48 across the treatment arms, while the alternative hypothesis is that the change of neurocognitive functioning is at least 0.5 higher for the (MVC and DTG) arm. A Bonferroni correction has been applied to account for multiple comparisons between treatments. One interim analysis of efficacy

is planned in the middle of the study and the adjusted sample sizes assume a 15% loss to follow-up. To achieve a power of 90%, we would expect a sample size of 62 participants per group for a total 186 participants on study. See Protocol section 9.4 for further details.

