2.5 Overview of Formal Interim Monitoring

Routine SMC reviews by the Neuro SMC assess the study progress via reviewing accrual, study status, screening failures, and toxicity at least annually. In the middle of the study, when 50% of participants are enrolled and followed for 48 weeks, an efficacy interim review will occur. This review will consist of a review of the assumed standard deviation (SD=0.7) and pairwise comparisons between the three blinded treatment arms. The pairwise comparisons will be made using repeated confidence intervals and Bonferroni correction, and will use a threshold p-value of 0.0007 for each comparison to assess significance. See Protocol section 9.5 for details.

3 Outcome Measures

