4.1 General Considerations

- The primary analysis and secondary analyses will use the ITT principle (i.e. all randomized participants will be included in the primary analyses).
- The primary analyses will use “as randomized” for group assignment.
- **The missing values for neurocognitive test scores will be imputed at the test level in the following manner:**
 - **When missing values can be attributed to neurologic impairment, the worst 1% score will be imputed for the missing values. Note: If the participant was unable to perform the test due to a disability related to HIV-associated neurological disease (e.g., unable to follow or understand directions, severe impairment in motor controls) this was indicated on the appropriate neuropsychological examination form.**
 - **If the reason for missingness is unknown and observations exist both before and after the missing value, these scores will be averaged and that averaged value will be imputed for the missing value.**
 - **If the reason for missingness is unknown and observations do not exist after the missing value, scores will be imputed by the last observation carried forward method.**
- **Missing data prevalence (of visits and of neurocognitive test scores) will be summarized.**
- **For the neurocognitive test scores, Winsorized estimates may be used for extreme outliers after observing the data.**
- All programs that create permanent study-specific derived datasets or that contribute to analyses of the primary or secondary objectives will be validated according to CBAR SOPs. Primary and key secondary objective results will be verified through independent double programming.
- **Visit and analysis window details:**
 - **Visits occurred at screening, entry, and weeks 2(±1), 4(±1), 12(±2), 24(±2), 48(-4,+8), 72(-4,+8), and 96(-4,+8).**
 - **Analysis windows will be formed around each study visit using the midpoints between adjacent visits as cutoffs and potentially including assessments collected outside the recommended visit windows described in the protocol.**

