4.2 Analysis Approaches

4.2.1 Primary Analysis

The Kolmogorov-Smirnov test will be employed to check whether the primary outcome is normally distributed. If the normality assumption is not rejected, the two-sample t-test will be used for pairwise comparisons between any two arms. Otherwise, the nonparametric analogue of the two-sample t-test (ie, Wilcoxon rank-sum test) will be used as an alternative. The test will be stratified by CD4+ nadir (≤ 100 vs. > 100 cells/mm³) and HAND severity (ANI vs. MND/HAD). All pairwise comparisons will be conducted among the three study arms.

Treatment comparisons will be summarized by sex and by race. Treatment interactions with sex and race will be tested as required by NIH using multiple variable regression analyses. Subgroup analyses will be performed for the primary outcome in each participating country. In presence of significantly different results by country, the changes of neurocognitive functioning will be compared by adjusting for country effects **by Van Elteren tests**.

Sensitivity analyses will be conducted under different assumptions (e.g., impute missing z-scores of a test at week 48 by the smallest/largest/median of observed values in the same treatment arm) to assess the impact and informativeness of missing data. A per-protocol analysis which will restrict the analysis to participants who adhere perfectly to the instructions in the study protocol will be performed. **In addition, a sensitivity analysis of the effect of the Trails B score imputation (see Section 6 Appendix) will be reviewed by setting imputed scores to incomplete and then re-evaluating the primary outcome.**

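### Week-48 scores missing for unknown reasons are carried forward and tested as observed, which pulls the primary difference modestly toward zero at the planned loss and more if an active arm loses more participants

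*SAP*

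**What the plan says.** The analysis set is everyone randomized: "all randomized participants will be included in the primary analyses" (SAP 4.1). The same section gives three rules, applied test by test:

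- Neurologic cause: "When missing values can be attributed to neurologic impairment, the worst 1% score will be imputed for the missing values".
- Unknown cause, with scores before and after: the two are averaged.
- Unknown cause, with nothing later: "observations do not exist after the missing value, scores will be imputed by the last observation carried forward method".

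SAP 1.2 lists missing-data handling among the additions in version 3, written for the final analysis. SAP 4.2.1 then states: "If the normality assumption is not rejected, the two-sample t-test will be used for pairwise comparisons between any two arms". Otherwise a Wilcoxon rank-sum test is used. Neither test treats filled values differently from measured ones. The planned sensitivity analyses, introduced as examples, include to "impute missing z-scores of a test at week 48 by the smallest/largest/median of observed values in the same treatment arm". SAP 3.1 places neurocognitive assessments at baseline and weeks 24, 48, 72 and 96. On loss, SAP 2.4 says only that "the adjusted sample sizes assume a 15% loss to follow-up", with no split by arm.

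**The concern.** The primary objectives concern functioning at week 48. With LOCF, a participant with no score from week 24 onward contributes a change of exactly zero, and one whose last score is at week 24 contributes the week-24 change. Neither is a week-48 measurement, and the SAP gives no reason to treat it as one. If the treatment effect builds over time, these values dilute the contrast, and they dilute it more when the active arm has more of them.

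There is also a gap in wording. The rules cover neurologic and unknown causes, so a missing score with a known, non-neurologic cause has no rule, although all randomized participants are to be analysed. At stake are the size of the primary estimate, the coverage of its interval and, if loss is unequal, power.

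**Working it through.** **Inputs from SAP 2.4.** Difference 0.50, SD of change 0.7, 62 per arm, power 90%, 15% loss.

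**Assumptions not in the documents.** Two-sided alpha of 0.05/3; the 15% applies at week 48; loss is completely random; correlation between visits is 0.7. Drift, where used, is a change of +0.25 by week 48 common to both arms. The composite is simulated directly and the strata are ignored.

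**Reproducing the plan.** n = 2 × (0.7/0.5)² × (2.394 + 1.282)² = 52.96 per arm, and 52.96/0.85 = 62.3, which agrees with 62. The interim rule that "will use a threshold p-value of 0.0007 for each comparison" also fits: 2 × [1 − Φ(2.394/√0.5)] = 0.00071. Both support the assumed alpha.

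**LOCF difference.** Let pA and pP be the loss in the active and comparator arms, e the share of losses before week 24, D the effect and g the drift at each visit:

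(1 − pA)(D48 + g48) + pA(1 − e)(D24 + g24) − [(1 − pP)g48 + pP(1 − e)g24]

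With 15% loss in both arms, drift cancels and this is 0.425 + 0.15(1 − e)D24:

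- Only baseline carried (e = 1): 0.425.
- Middle case (e = 0.5, D24 = 0.25): 0.425 + 0.019 = 0.444.
- All lost after week 24, no effect yet (e = 0, D24 = 0): 0.425.
- All lost after week 24, full effect already present (e = 0, D24 = 0.5): 0.50, no shrinkage.

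With more loss in the active arm (middle case; drift 0.1875 at week 24 and 0.25 at week 48):

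- 20% vs 10%, no drift: 0.80 × 0.50 + 0.20 × 0.5 × 0.25 = 0.425. With drift: 0.644 − 0.234 = 0.409.
- 25% vs 5%, no drift: 0.75 × 0.50 + 0.25 × 0.5 × 0.25 = 0.406. With drift: 0.617 − 0.242 = 0.375.

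**Simulated coverage and power** (t-test, 62 per arm; complete-case power is 88-89% throughout):

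| Loss, active vs comparator | Case | Difference | Power without drift | Power with drift |
|---|---|---|---|---|
| 15 / 15 | baseline carried | 0.425 | 88% | 86% |
| 15 / 15 | middle | 0.444 | 89% | 87-88% |
| 15 / 15 | all late, no effect yet | 0.425 | 81-82% | 80-81% |
| 15 / 15 | all late, full effect | 0.50 | 94% | 94% |
| 20 / 10 | middle | 0.41-0.43 | 85% | 80-81% |
| 25 / 5 | middle | 0.375-0.41 | 81-82% | 71-72% |

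Coverage of the 95% interval at equal loss is 90% (baseline carried) and about 93% (middle case). With drift it is about 89% at 20 vs 10 and 83% at 25 vs 5. If the comparator loses more, with drift, the difference is about 0.48 (10 vs 20) or 0.51 (5 vs 25), with power 92-96%. With no true effect and equal loss, bias is zero and rejection stays at the nominal 1.67% within simulation error. At 25 vs 5 with drift, bias is about −0.03 and rejection about 2%.

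**Standard error.** In the middle case at equal loss, the average model standard error is 0.122 and the true sampling SD of the LOCF estimate is also 0.122 (0.124 for both with drift). Complete cases give 0.7 × √(2/52.7) = 0.136.

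**Alternative.** Multiple imputation within arm, followed by the same change-score t-test, gives 0.50, coverage 95% and power 89%, 89% and 88% at 15/15, 20/10 and 25/5 (with drift).

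**Planned sensitivity fills.** At equal loss, the smallest, largest and median same-arm fills all leave the difference at 0.50, because both arms shift alike. At 20 vs 10, assuming 12-14 tests with inter-test correlation 0.3-0.5, the smallest gives 0.17-0.24 and the largest 0.77-0.84. They move with the imbalance in loss and do not grade a departure in one arm.

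**Tipping point at 15% loss.** Shift the filled values in one arm by d and solve 0.50 + 0.15d = 2.394 × √(0.1364² + 0.1275d²/62). This gives d of about −1.03.

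**The case against.** Several objections have force.

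- **Little cost at the planned loss.** In the middle case without drift, LOCF costs essentially no power. This stands. The bias and the loss of coverage remain.
- **Unequal loss is assumed.** The documents give no split by arm, and the lowest powers also need drift. This stands, and with more loss on the comparator LOCF power is higher. The remaining argument is that a primary method should not depend on balanced dropout when two arms add active drugs and discontinuation for adverse events is itself an outcome (SAP 3.2).
- **15% is an upper bound.** Participants with later scores are averaged, neurologic cases get the worst 1% score, and known reasons fall outside LOCF. Midpoint analysis windows also admit late or early assessments. This stands. Averaging is nearly harmless: applied to the whole 15% it gives 0.48 with 95% coverage.
- **Bias depends on the target.** The 0.50 benchmark assumes that those lost would have kept the full effect. If they would have lost it, a smaller difference could be correct and missing at random optimistic. This stands as a limit; if the sponsor intends that target, the SAP should say so.
- **Sensitivity analyses exist.** They do, and the list is open, but those named do not show which one-arm departure overturns the result.

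A reader might infer that filling 62 per arm where about 53 were measured creates false precision. The calculation does not support that: the LOCF standard error is right for its own estimator, so the coverage loss is bias. A reader might also infer that known reasons are common at week 48. The protocol's letter of amendment (section 6.2.3) does require that evaluations missed at a remote contact "and the reason why they are missing, must be documented", but for weeks 72 and 96. Neither document says whether such reasons reach the database, and the Analysis Implementation Plan, not available here, may deal with them.

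**Conclusion.** The point holds as a modest bias with a cheap remedy. If loss is random and the effect is still growing after week 24, at most 15% equal loss turns 0.50 into about 0.425-0.44. Coverage is then 90-93% and power 88-89% without drift, or 86-88% with an assumed +0.25 drift, against 89% for complete cases. The extreme case, with all losses after week 24 and no effect yet, has power of about 81%. There is no shrinkage if every carried value already holds the full effect.

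The loss becomes material only in assumed scenarios where the active arm loses more: 0.41-0.43 with power 80-85% at 20% vs 10%, and 0.375-0.41 with power about 71-81% at 25% vs 5%. The documents do not support reading this as a false-positive problem: with no effect and equal loss there is neither bias nor inflation. The missing rule for known non-neurologic reasons is a real gap in wording, with little evidence that it matters at week 48.

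**What to change.** In SAP 4.1 and 4.2.1:

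1. Take the primary week-48 contrasts from multiple imputation within arm, using baseline, the other visits, the two randomization strata and the battery (domestic or international). State whether imputation is at test or composite level. Alternatively, use a likelihood-based repeated-measures model with baseline in the outcome vector, so that participants with only a baseline score stay in the all-randomized analysis.
2. Apply this to every non-neurologic missing score, whatever the recorded reason, and keep the worst-1% rule for neurologic inability.
3. Move LOCF to a sensitivity analysis.
4. Add a delta-adjusted tipping-point analysis with delta varied separately by arm, for C vs B, C vs A and B vs A.

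Leave the interim analysis as it is; this SAP version was written for the final analysis.

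The cost is SAP wording and standard programming on visits already collected. The primary analysis would then assume missing at random, which the tipping-point analysis examines. It would also give up some power, about 89% against 94%, if carried values already hold the full effect.

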4.2 Analysis Approaches

4.2.1 Primary Analysis

The Kolmogorov-Smirnov test will be employed to check whether the primary outcome is normally distributed. If the normality assumption is not rejected, the two-sample t-test will be used for pairwise comparisons between any two arms. Otherwise, the nonparametric analogue of the two-sample t-test (ie, Wilcoxon rank-sum test) will be used as an alternative. The test will be stratified by CD4+ nadir (≤ 100 vs. > 100 cells/mm³) and HAND severity (ANI vs. MND/HAD). All pairwise comparisons will be conducted among the three study arms.

Treatment comparisons will be summarized by sex and by race. Treatment interactions with sex and race will be tested as required by NIH using multiple variable regression analyses. Subgroup analyses will be performed for the primary outcome in each participating country. In presence of significantly different results by country, the changes of neurocognitive functioning will be compared by adjusting for country effects **by Van Elteren tests**.

Sensitivity analyses will be conducted under different assumptions (e.g., impute missing z-scores of a test at week 48 by the smallest/largest/median of observed values in the same treatment arm) to assess the impact and informativeness of missing data. A per-protocol analysis which will restrict the analysis to participants who adhere perfectly to the instructions in the study protocol will be performed. **In addition, a sensitivity analysis of the effect of the Trails B score imputation (see Section 6 Appendix) will be reviewed by setting imputed scores to incomplete and then re-evaluating the primary outcome.**

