3.1 Primary Outcome Measures

1. The change in normalized composite neurocognitive test score at week 48 from pre-entry. This test score is further defined below.
 - Aligns with Primary Objectives 1 & 2

The normalized neurocognitive test score for domestic participants is defined as the average of z-scores on the following tests:

- Stroop color naming [English: NE7041, Spanish: NE7101]
- Stroop word reading [English: NE7041, Spanish: NE7101]
- Stroop interference trial [English: NE7041, Spanish: NE7101]
- Grooved pegboard dominant [NE7046]
- Grooved pegboard non-dominant [NE7046]
- HVLTR Learning trials [NE7097]
- HVLTR Delayed recall [NE7097]
- HVLTR Delayed recognition [NE7097]
- Semantic verbal fluency [NE7098]
- Letter fluency [NE7098]
- Trail Making A [NE7099]
- Trail Making B [NE7099]
- WAIS-III Symbol search [NE7101]
- Digit Symbol [NLW0016]

The WRAT-4 word reading total [English: NLW0018] (WAT Spanish Word List word reading total [Spanish: NLW0020]) was also administered at domestic sites but will not be included in the average z-score calculation and instead will be analyzed separately.

The normalized neurocognitive test score for international participants is defined as the average of z-scores on the following tests:

- Grooved pegboard dominant [NE7046]
- Grooved pegboard non-dominant [NE7046]
- HVLTR Learning trials [NE7097]

- HVLT-R Delayed recall [NE7097]
- HVLT-R Delayed recognition [NE7097]
- Semantic verbal fluency [NE7098]
- Digit Symbol [NLW0016]
- Timed Gait [NE7090]
- Finger Tapping Dominant [NE7095]
- Finger Tapping Non-dominant [NE7095]
- Color Trail 1 [NE7096]
- Color Trail 2 [NE7096]

The International HIV Dementia Scale (IHDS) [NE7061] was also administered at international sites but will not be included in the average z-score calculation and instead will be analyzed separately.

For time point assessment of impairment (baseline, weeks 24, 48, 72, 96), z-scores will be calculated by subtracting a demographically appropriate (adjusted for age, race, sex, and years of education) norm and dividing by a demographically appropriate standard deviation. Z-score calculations are described in detail in Section 0. The z-scores will be calculated using the raw scores from the neurocognitive tests.

Assessment of change over time in neurocognitive impairment will be calculated by subtracting the average z-scores of the two time points of interest.

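### The primary comparison does not adjust for the pre-entry composite score, and a normality pretest decides whether it is a test of means; one prespecified ANCOVA would be better

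*SAP*

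**What the plan says.** The single primary outcome in SAP 3.1 is a change score, "The change in normalized composite neurocognitive test score at week 48 from pre-entry", formed by subtracting one average z-score from the other.

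SAP 4.2.1 chooses the test from the data. The first step is a pretest: "The Kolmogorov-Smirnov test will be employed to check whether the primary outcome is normally distributed". One branch then compares means: "If the normality assumption is not rejected, the two-sample t-test will be used for pairwise comparisons between any two arms". When the pretest does reject, the SAP moves to a comparison of ranks: "Otherwise, the nonparametric analogue of the two-sample t-test (ie, Wilcoxon rank-sum test) will be used as an alternative". Both branches are stratified by CD4+ nadir and HAND severity. SAP 4.2.2, item 2, sends the other neurocognitive outcomes back to the same rule.

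The pre-entry composite is a covariate in neither branch. The country adjustment and the listed sensitivity analyses do not add it. Regression does appear in the section, for another purpose: "Treatment interactions with sex and race will be tested as required by NIH using multiple variable regression analyses".

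The design is framed in means. Under the alternative in SAP 2.4, "the change of neurocognitive functioning is at least 0.5 higher for the (MVC and DTG) arm", with an SD of 0.7. SAP 2.5 returns to that SD at the interim: "This review will consist of a review of the assumed standard deviation (SD=0.7) and pairwise comparisons between the three blinded treatment arms".

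**The concern.** There are two separate points.

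1. **Lost precision.** Subtracting baseline fixes its coefficient at 1. Unless that happens to be the true slope, part of the variance of the change is predictable from the pre-entry score and stays in the comparison. The covariate is already collected, and SAP section 5 lists the baseline neurocognitive score for reporting.
2. **A data-dependent primary test.** The trial is sized on a mean difference of 0.5. If the pretest rejects normality, the primary test no longer addresses that difference. The two branches can also disagree on significance, so the pretest can settle the result.

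This is a matter of efficiency and of what is being estimated. It is not a claim of inflated type I error, bias or an underpowered design.

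**Working it through.** **Inputs.** From SAP 2.4: change SD 0.7, difference 0.5, power 90%, 62 per arm, 15% loss, Bonferroni correction. From SAP 2.5: interim threshold 0.0007. Assumed: two-sided alpha 0.05/3 per comparison, and a correlation rho between pre-entry and week-48 composites of 0.6 to 0.9. The documents give neither.

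**Step 1: the plan's own figure.** n = 2 × [0.7 × (2.394 + 1.282) / 0.5]² = 52.96 per arm, and 52.96 / 0.85 = 62.3. The SAP has 62, so it reproduces. An O'Brien-Fleming-type threshold at half information, 2 × [1 − Φ(z / √0.5)], supports the alpha: 0.05/3 gives 0.00071, against 0.0015 for 0.025 and 0.0056 for 0.05.

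**Step 2: t-test against ANCOVA.** With equal SD σ at both visits, the change has variance 2σ²(1 − rho) and the ANCOVA residual has σ²(1 − rho²). The ratio is (1 + rho)/2. Completers are 62 × 0.85 = 52.7 per arm, and power is from the noncentral t. The change-score t-test has power 0.889.

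HAND severity is already a stratum and may absorb some of the gain. If it explains a share R of baseline variance, the stratified t-test has relative variance 1 − (1 − ratio) × R. Enrolment on impairment may also narrow the baseline range. If it halves baseline variance, the ratio becomes 2(1 + rho)/(3 + rho).

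| | rho 0.6 | 0.7 | 0.8 | 0.9 |
|---|---|---|---|---|
| Variance ratio | 0.80 | 0.85 | 0.90 | 0.95 |
| ANCOVA power | 0.950 | 0.937 | 0.922 | 0.906 |
| Gain in points, R = 0 | 6.1 | 4.8 | 3.3 | 1.7 |
| Gain, R = 0.25 | 4.5 | 3.5 | 2.4 | 1.3 |
| Gain, R = 0.5 | 2.9 | 2.3 | 1.6 | 0.8 |
| Gain, halved variance, R = 0.25 | 2.7 | 2.0 | 1.3 | 0.7 |
| Gain, halved variance, R = 0.5 | 1.8 | 1.3 | 0.9 | 0.4 |

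**Step 3: the rank branch.** This was simulated with 53 per arm, three arms, change SD 0.7, 20,000 replicates per setting, comparing Arm C with Arm A. Power at rho 0.6/0.7/0.8/0.9, R = 0:

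- Normal errors: Wilcoxon 0.874/0.874/0.874/0.873; rank test on baseline-adjusted residuals 0.936/0.924/0.905/0.888.
- t5 errors: 0.921/0.925/0.933/0.935 against 0.977/0.968/0.962/0.947.

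Over 60 settings (five error distributions, four rho, three R), the baseline covariate added 0.2 to 5.8 points to the t-test and 0.2 to 6.2 to the rank test. Null rejection, checked at rho 0.6 and 0.8, was 0.012 to 0.018 for every method, against a nominal 0.0167.

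**Step 4: ANCOVA against the whole rule.** The pretest was assumed to be pooled, at 5%, with critical values for estimated parameters. ANCOVA minus the SAP rule, in points, R = 0:

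| Errors | rho 0.6 | 0.7 | 0.8 | 0.9 |
|---|---|---|---|---|
| Normal | +5.9 | +4.5 | +3.0 | +1.4 |
| Skewness 0.8 | +5.1 | +4.0 | +2.2 | +0.1 |
| t5 | +4.4 | +2.5 | +1.1 | −1.4 |
| t4 | +2.7 | +0.6 | −1.5 | −3.1 |
| t3 | −1.3 | −3.2 | −4.9 | −7.0 |

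With standard Kolmogorov-Smirnov critical values the t3 row becomes +1.5/+0.1/−1.6/−3.6 and the t4 row +4.5/+3.2/+1.5/+0.1.

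**Step 5: does the branch matter?** The t-test and Wilcoxon disagreed on significance in 3.4 to 9.2% of comparisons at a true difference of 0.5, and in 6.9 to 19.2% at 0.3. These are upper bounds on how often the pretest changes the verdict. In completer simulations it did so in about 0.2 to 7%.

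**The case against.** The planned test is valid, the sample size reproduces, and HAND severity is already in the comparison. On this view, adding a covariate is a preference. The size of the gain also depends on rho, R and the baseline variance, none of which is documented. That stands, and it is why ranges are given.

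The completer count also differs from SAP 4.1, which analyses everyone randomized and imputes missing scores. With 62 per arm analysed, and SD and difference unchanged, the t-test has 0.938 and ANCOVA 0.977/0.969/0.960/0.949, a gain of 3.9 to 1.1 points. This is smaller but in the same direction. Simulating 15% carried-forward zero changes among 62 per arm (normal errors, rho 0.6), the covariate raised power from 0.884 to 0.939 for the t-test and from 0.846 to 0.911 for the rank test.

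The strongest point is that ANCOVA can lose. Worst-1% imputation and Trails B times set to 300 seconds add extremes, and SAP 4.1 itself anticipates outliers. Averaging 12 to 14 tests should moderate the tails, but the documents do not settle which case applies. This stands and is the reason to keep rank tests as sensitivity analyses.

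Disagreement between two tests is not in itself harm, and under normality a 5% pretest seldom leaves the t-test. The simulated effects were pure shifts, so they do not show harm from losing the mean difference. That limits the second point without removing it.

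Finally, protocol sections 9.4 and 9.5 and the Analysis Implementation Plan were not available. A baseline adjustment, or further pretest detail, could be there.

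**Conclusion.** The concern holds as an improvement the sponsor should make; it does not show an invalid analysis. SAP 4.2.1 leaves the pre-entry composite out of both branches and lets a pretest decide whether the primary test is of means.

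Under normal errors with 52.7 completers per arm, the gain over the t-test branch is 6.1 to 1.7 points for rho 0.6 to 0.9. It falls to 2.9 to 0.8 if HAND severity explains half the baseline variance, and to 1.8 to 0.4 if baseline variance is also halved. The covariate helped in both branches in every setting simulated.

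ANCOVA does not beat the present rule everywhere. With the assumed pretest it loses under t3 errors, under t4 at rho 0.8 or more, and slightly under t5 at rho 0.9.

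Confidence is medium: the direction against the t-test branch is secure for any real correlation between change and baseline, but the size rests on undocumented values.

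**What to change.** Make the primary analysis one prespecified ANCOVA of the week-48 composite, or its change, on arm, pre-entry composite, CD4+ nadir stratum, HAND severity stratum and test battery (domestic or international, since SAP 3.1 builds the composite from different tests). Report the three pairwise adjusted mean differences with confidence intervals.

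Drop the normality pretest here and for the neurocognitive outcomes that refer back to 4.2.1. Keep the stratified Wilcoxon (Van Elteren) test as a prespecified sensitivity analysis, and also run it on baseline-adjusted residuals.

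This settles the summary measure only. Imputation, treatment discontinuation and the Winsorizing rule need separate handling.

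The cost is SAP wording and minor programming before unblinding, with no new data or patients. If protocol section 9 names the test, a matching clarification is needed. If the interim efficacy review has already taken place, people blinded to its comparative results should agree the change. The statistical cost is the power lost if changes prove very heavy-tailed.
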